## 1. Synopsis

### Title of Study:

A Prospective, Randomized, Double-Blind Comparison of LY900014 to Humalog with an Open-Label Postprandial LY900014 Treatment Group in Children and Adolescents with Type 1 Diabetes: PRONTO-Peds

### Rationale:

The aim of this study is to demonstrate that an ultra-rapid formulation of insulin lispro, LY900014, is noninferior to Humalog on glycemic control as measured by change from baseline to Week 26 in hemoglobin A1c (HbA1c) in pediatric patients with type 1 diabetes (T1D), when administered in a double-blind manner as prandial insulin (0 to 2 minutes prior to the meal) in combination with basal insulin.

### Objectives/Endpoints:

Objectives	Endpoints
Primary Objective	
1. To test the hypothesis that LY900014 is noninferior to Humalog on glycemic control (NIM=0.4% for HbA1c) in patients 1 to <18 years of age with T1D when administered as prandial insulin (0 to 2 minutes prior to the meal) in combination with basal insulin as part of a multiple daily injection regimen for 26 weeks	1. Difference between LY900014 and Humalog in change from baseline to Week 26 in HbA1c
Gated Objective	
2. To test the hypothesis that LY900014 administered as postprandial insulin up to 20 minutes after the start of a meal (LY900014+20) is noninferior to Humalog, administered as prandial insulin (0 to 2 minutes prior to the meal), on glycemic control (NIM=0.4% for HbA1c)	2. Change from baseline to Week 26 in HbA1c
3. To test the hypothesis that LY900014 is superior to Humalog in improving glycemic control (HbA1c) when administered as prandial insulin (0 to 2 minutes prior to the meal)	3. Difference between LY900014 and Humalog in change from baseline to Week 26 in HbA1c
Other Secondary Objectives	
4. To compare LY900014, LY900014+20, and Humalog with respect to the incidence and rate of documented post-dose hypoglycemia	4. Rate (events/patient/year) and incidence (percentage of patients with events) of documented post-dose hypoglycemic events within 1 and 2 hours after the prandial dose from Weeks 0 through 26
5. To compare LY900014, LY900014+20, and Humalog with respect to the incidence and rate of documented hypoglycemia	5. Rate (events/patient/year) and incidence (percentage of patients with events) of documented hypoglycemic events from Weeks 0 through 26

6. To compare LY900014, LY900014+20, and Humalog on the rate of severe hypoglycemic events	6. Rate (events/patient/100 years) of severe hypoglycemic events from Weeks 0 through 26
7. To compare LY900014, LY900014+20, and Humalog with respect to total, basal, and prandial insulin dose	7. Change from baseline in total, basal, and prandial insulin doses and prandial/total insulin dose ratios at Week 26
8. To compare LY900014, LY900014+20, and Humalog with respect to the proportion of patients achieving HbA1c targets	8. The proportion of patients with HbA1c <7% and <7.5% at Week 26
9. To compare LY900014, LY900014+20, and Humalog with respect to 7-point SMBG	9. Change from baseline to Week 26 in 7-point SMBG values

Abbreviations: HbA1c = hemoglobin A1c; NIM = noninferiority margin; SMBG = self-monitored blood glucose; T1D = type 1 diabetes.

### Summary of Study Design:

Study I8B-MC-ITSB (ITSB) is a Phase 3, prospective, randomized, outpatient, multinational, multicenter, parallel, active-controlled study conducted in children and adolescent patients with T1D currently using a multiple-daily-injection (MDI) regimen.

### Treatment Arms and Duration:

The study includes a 1-week screening with a 4-week lead-in period, followed by a 26-week treatment period and a 2-week safety follow-up period. In 2 of the treatment groups, LY900014 and Humalog will be administered immediately (0 to 2 minutes) prior to each meal in a double-blind manner. A third open-label treatment group consists of LY900014 administered up to 20 minutes after the start of a meal (LY900014+20).

### Number of Patients:

Approximately 945 participants will be screened to achieve 708 randomized and 600 patients completing 26 weeks of treatment for an estimated total of 240 completers per blinded treatment group and 120 completers for the open-label treatment group.

### Statistical Analysis:

The primary analysis is for the treatment period through Week 26.

Efficacy analyses will be conducted on all randomized patients according to the treatment the patients are assigned. The analyses for the primary and gated objectives will be performed for the efficacy estimand, including data collected prior to permanent discontinuation of investigational product (IP) and for the intention-to-treat (ITT) estimand, including all data collected regardless of IP use. The primary endpoint will also be analyzed using the Per-Protocol (PP) and Completer populations.

Safety analyses will be conducted on the Safety population. Analyses of adverse events (AEs) will include 2 sets of analyses, unless otherwise specified. The first set of analyses will include data collected prior to permanent discontinuation of IP. The second set of analyses will include

all data collected during the course of the entire study, including the follow-up visit, regardless of IP use. Analyses of hypoglycemia will use data collected prior to permanent discontinuation of IP, while analyses for post treatment may be performed as needed. Analyses of safety laboratory measurements will be performed on all data during the planned treatment period regardless of IP use.

Baseline is defined as the last non-missing measurement at or before the randomization visit (Visit 4), unless otherwise specified.

For the United States (US) Food and Drug Administration (FDA) submission (using the ITT estimand), the missing endpoints will be imputed by the copy reference approach. The reference for each treatment group is from the retrieved dropout patients who discontinue IP but have the measurement at the primary endpoint in the same treatment group. If there are only a limited number of patients in the reference group that leads to a failure in performing the proposed multiple imputation analysis such that the model cannot converge, or the number of records in the reference group is less than the number of records with missing data, the missing endpoints will be imputed by the patient-level observed baseline value plus a noise, assuming a washout of any potential treatment effect (or “return to baseline”). The noise follows a normal distribution, with the variability estimated from the “washout HbA1c data”. The “washout HbA1c data” will be derived by subtracting the corresponding treatment mean at Week 26 from individual non-missing HbA1c values at Week 26. After imputation, the primary efficacy comparison will be based on the contrast between LY900014 and Humalog from an analysis of covariance (ANCOVA). The model for the change from baseline to the Week 26 HbA1c endpoint will include treatment and strata (pooled country, type of basal insulin, and age group) as fixed effects and baseline HbA1c as a covariate. The final estimates will be the combined estimates from at least 1000 imputations.

For non-FDA submissions and publications, the primary efficacy comparison will be based on the contrast between LY900014 and Humalog at Week 26 (Visit 15) from the mixed-effect model repeated-measure (MMRM) analysis of change from baseline in HbA1c, including data collected from all randomized patients prior to permanent discontinuation of IP through Week 26 (efficacy estimand).

For both primary analysis approaches, LY900014 will be declared noninferior to Humalog if the upper limit of the 2-sided 95% confidence interval (CI) for the least-squares (LS) mean difference in the change from baseline in HbA1c for LY900014 minus Humalog is below +0.4%. In addition, the 95% CI for the treatment difference will be compared to an alternative NIM of +0.3%. Both estimands will be tested at the full significance level of 0.05.

A restricted maximum likelihood-based MMRM analysis will be used to analyze continuous longitudinal variables. All the longitudinal observations at each scheduled postbaseline visit will be included in the analysis. The model for the analysis of the primary efficacy endpoint of change from baseline in HbA1c will include the fixed class effects of treatment, strata (pooled country, type of basal insulin, and age group), visit, and treatment-by-visit interaction, as well as the continuous, fixed covariate of baseline value. For analyses of variables other than HbA1c,

the HbA1c stratum ( $\leq 8.0\%$ ,  $> 8.0\%$ ) will be included in the model. An unstructured covariance structure will be used to model the within-patient errors. Significance tests will be based on LS means and Type III tests.

An ANCOVA will also be used to analyze continuous variables. The model for the change from baseline to the Week 26 HbA1c endpoint will include treatment and strata (pooled country, type of basal insulin, and age group) as fixed effects and baseline as a covariate. Unless otherwise stated, missing endpoints will be imputed using the last-observation-carried-forward (LOCF) approach, using only postbaseline data. For analyses of variables other than HbA1c, the HbA1c stratum ( $\leq 8.0\%$ ,  $> 8.0\%$ ) will be included in the model.

Hypoglycemia rates will be summarized for periods of 30 days, 1 year, and 100 years (severe hypoglycemia only). The rate of severe hypoglycemia per 100 years will be compared between treatment groups using the empirical method (details will be described in statistical analysis plan [SAP]). For each of the other categories of hypoglycemia, the number of hypoglycemia events during a specific period after randomization (for example, Weeks 0 to 12 of treatment period) will be analyzed by using a negative binomial regression model. The model will include treatment and age group as covariates. An offset defined as the log transformation of treatment exposure in the specific period (days)/365.25 days (or 30 days) will be included in the model to estimate the rate of hypoglycemia per year (or per 30 days). The proportion of patients with at least 1 hypoglycemic event in each category during a specific period after randomization will be analyzed using a logistic regression model including treatment and age group as covariates.

Continuous safety variables, as well as the change from baseline for these variables, will be analyzed by MMRM or ANCOVA models. For categorical variables, Fisher's exact test or Pearson's chi-square test will be used to compare treatment groups, unless otherwise specified.

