## 10. Statistical Considerations

### 10.1. Sample Size Determination

Approximately 708 patients will be randomized in order that 600 patients complete the study through the primary endpoint at Week 26.

Patients will be randomized in a 2:2:1 ratio to double-blind LY900014 dosed 0 to 2 minutes before meals, double-blind Humalog dosed 0 to 2 minutes before meals, or open-label LY900014 dosed up to 20 minutes after the start of a meal. Stratification will be by country, HbA1c stratum ( $\leq 8.0\%$ ,  $> 8.0\%$ ), type of basal insulin (insulin glargine, insulin detemir, or insulin degludec), and age group (1 to  $< 12$  years, 12 to  $< 18$  years).

Assuming a NIM of 0.4%, no true difference between treatment groups and an SD of 1.1%, 240 completers for each double-blind treatment group will provide greater than 95% power to show noninferiority between LY900014 and Humalog using the upper limit of a 2-sided 95% CI (LY900014–Humalog). This sample size also has more than 80% power to show noninferiority between LY900014 and Humalog using a 0.3% NIM at 26 weeks.

With the assumption a difference no larger than 0.07% between treatment groups and a SD of 1.1%, 240 completers of double-blind Humalog dosed 0 to 2 minutes before meals and 120 completers of open-label LY900014 dosed up to 20 minutes after the start of a meal will provide approximately 76% power to show noninferiority between open-label LY900014+20 and double-blind Humalog using a NIM of 0.4%.

Assuming a 15% dropout rate during 26 weeks of treatment, approximately 708 patients (283 patients in each double-blind treatment group and 142 patients in the open-label treatment group) will need to be randomized.

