#### **10.3.4. Safety Analyses**

Safety measures will include AEs, hypoglycemia, vital signs and weight, treatment exposure, laboratory measures, and antibodies to insulin lispro. Analyses will be performed on data collected from randomization through Visit 801 for both treatment groups.

Events that are newly reported after the first dose of IP or reported to worsen in severity from baseline will be considered treatment-emergent AEs (TEAEs). The Medical Dictionary for Regulatory Activities (MedDRA) lowest level term (LLT) will be used in the treatment-emergent assessment. The maximum severity for each LLT during the baseline period will be used as baseline severity.

The SAEs, AEs reported as reason for discontinuation from the IP or study, and TEAEs will be summarized in tables using the MedDRA PT, sorted by decreasing frequency within the LY900014 treatment group. The TEAEs will also be summarized by PT sorted by decreasing frequency within SOC for all TEAEs and by maximum severity. For events that are specific to only 1 sex, the denominator and computation of the percentage will include only patients from

the given sex. The number and proportion of patients with at least 1 event for each type of event will be summarized and compared between treatment groups using Fisher's exact test.

Hypoglycemia rates will be summarized for periods of 30 days, 1 year, and 100 years (severe hypoglycemia only). The rate of severe hypoglycemia per 100 years will be compared between treatment groups using the empirical method (details will be described in SAP). For each of the other categories of hypoglycemia, the number of hypoglycemia events during a specific period after randomization (for example, Weeks 0 to 12 of treatment period) will be analyzed by using a negative binomial regression model. The model will include treatment and age group as covariates. An offset defined as the log transformation of treatment exposure in the specific period (days)/365.25 days (or 30 days) will be included in the model to estimate the rate of hypoglycemia per year (or per 30 days). The proportion of patients with at least 1 hypoglycemic event in each category during a specific period after randomization will be analyzed using a logistic regression model including treatment and age group as covariates.

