Efficacy analyses will be conducted on all randomized patients according to the treatment the patients are assigned. The analyses for the primary and gated objectives will be performed for the efficacy estimand including data collected prior to permanent discontinuation of investigational product (IP) and for the intention-to-treat (ITT) estimand including all data collected regardless of IP use. The primary endpoint will also be analyzed using the Per Protocol (PP) and Completer populations.

Unless otherwise specified, the efficacy analyses for other secondary objectives and exploratory objectives will be performed for the efficacy estimand. When change from baseline is included as a response variable of analysis models, the patient will be included in the analysis only if a baseline and at least 1 postbaseline measurement are available, except for the analysis for ITT estimand on primary endpoint. The analysis for the ITT estimand will include all randomized patients with a baseline.

Safety analyses will be conducted on the Safety Population. Analyses of adverse events (AEs) will include 2 sets of analyses, unless otherwise specified. The first set of analyses will include data collected prior to permanent discontinuation of IP. The second set of analyses will include all data collected during the course of the entire study including the follow-up visit, regardless of IP use. Analyses of hypoglycemia will use data collected prior to permanent discontinuation of IP; while analyses for post-treatment may be performed as needed. Analyses of safety laboratory measurements will be performed on all data during the planned treatment period regardless of IP use.

The data on IP is defined based on the following rules:

- For data only measured at an office visit (for example, vital signs, safety laboratory tests, and questionnaires) will be considered as on IP if the measurement was performed at or prior to the cutoff date defined as 14 days after the last IP dose date
- For data collected as running records with an exact date stamp such as AEs and hypoglycemia events from patient diary where the dates of the measures were not tied with the date of an office visit, postbaseline data with dates \leq (last study drug dose date +1 day) will be considered as data on IP.
- For insulin dose data including both basal and prandial insulin dose, the dose used between the first IP dose date and the last IP dose date will be considered as data on IP.

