Rate of hypoglycemic events (per patient per year) All Documented ^a Nocturnal ^a Non-Nocturnal (Documented and occurred between waking and bedtime) ^a	0-12, 0-26weeks	Negative binomial regression with treatment and age group as covariates, log (exposure/365.25 days) as the offset in the model.
Incidence of hypoglycemic events All Documented ^a Nocturnal ^a Non-Nocturnal (Documented and occurred between waking and bedtime) ^a	0-12, 0-26weeks	Logistic regression with treatment and age group as covariates.
Rate of post-dose hypoglycemic events (per patient per year) for all 3 main meals All Documented ^a	≤1, ≤2, ≤4, >4, and >2 to ≤4 hours after start of prandial insulin dose within 0-12, 0-26,weeks	Negative binomial regression with treatment and age group as covariates, log (exposure/365.25 days) as the offset in the model.
Incidence of post-dose hypoglycemic events for all 3 main meals All Documented ^a	≤1, ≤2, ≤4, >4, and >2 to ≤4 hours after start of prandial dose within 0-12, 0-26,weeks	Logistic regression with treatment and age group as covariates.
Rate of severe hypoglycemic events (per patient per 100 years)	0-12, 0-26weeks	Exposure adjusted rate 100 years (calculated by total number of events divided by total exposure for individual patients) will be provided and the empirical method (see Appendix 1 for details) will be used for treatment comparison.
Incidence of severe hypoglycemic events	0-12, 0-26weeks	Proportion of patients with severe hypoglycemia will be reported. The treatment comparison will be based on a logistic regression model with treatment and age group as covariates.

^a All documented hypoglycemia and the subcategories based on the thresholds of blood glucose ≤70 mg/dL and blood glucose <54 mg/dL will be analyzed.

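### Hypoglycemia incidence is tested without regard to time on IP, so a patient who stops early with no prior event counts as a non-event for the whole window

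*Protocol*

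**What the plan says.** Secondary objectives 4 and 5 each pair a rate with an incidence over Weeks 0 to 26. For objective 4 the second half is the "incidence (percentage of patients with events) of documented post-dose hypoglycemic events" within 1 and 2 hours of the prandial dose.

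- **Data.** Protocol synopsis: "Analyses of hypoglycemia will use data collected prior to permanent discontinuation of IP". SAP 5.1 counts diary events up to one day after the last dose. Analyses of the period after IP are optional in both documents.
- **Denominator.** SAP Table ITSB.5.2 assigns hypoglycemia to the Safety population, which is everyone randomized who took at least one dose. Early stoppers stay in.
- **Incidence model.** Protocol synopsis, repeated in 10.3.4: the share of patients with any hypoglycemia "in each category during a specific period after randomization will be analyzed using a logistic regression model including treatment and age group as covariates". SAP Table ITSB.5.4: "Logistic regression with treatment and age group as covariates", for 0-12 and 0-26 weeks, including the post-dose categories. For severe events the table says: "The treatment comparison will be based on a logistic regression model with treatment and age group as covariates". None of these has an offset, censoring or imputation.
- **Rate model.** For the same non-severe events, the negative binomial model carries log exposure as an offset. The severe rate is total events over total exposure.

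**The concern.** A percentage of patients with an event over 26 weeks is naturally read as a 26-week risk. Here a patient who leaves IP in Week 3, having had no event, supplies three weeks of observation and is entered as 26 event-free weeks. The plan allows for unequal exposure in the rate half of each objective but not in the incidence half.

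Two consequences follow. First, every arm's percentage is too low as an estimate of on-treatment incidence over the window. Second, if one arm loses time on IP faster than another, the odds ratio moves in that arm's favor even when the underlying risk is the same, provided stopping is unrelated to hypoglycemia. Hypoglycemia is a main safety comparison for a faster insulin, and each incidence is compared between arms at a two-sided 0.05 level.

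**Working it through.** **The plan's own figure.** Protocol 10.1: "Assuming a 15% dropout rate during 26 weeks of treatment". 240/0.85 = 282.4, so 283 per blinded arm; 120/0.85 = 141.2, so 142 in the open-label arm; 283 + 283 + 142 = 708. This reproduces. One dropout rate is applied to all arms.

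**Assumed inputs.** The documents give no hypoglycemia rate, no split of dropout by arm and no stopping times. I assume that:

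- the 15% can be read as permanent IP stopping, although a patient may stop IP and remain in the study;
- stopping is uniform over 26 weeks and unrelated to hypoglycemia;
- true 26-week on-treatment incidence p lies between 20% and 90%;
- risk is identical in both arms.

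**Formula.** Let d be the fraction who stop IP and q the mean probability that a stopper had an event before stopping. The expected reported incidence is (1 − d)·p + d·q.

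- Constant hazard: H = −ln(1 − p), and q = 1 − p/H.
- Gamma frailty with variance 1 (patients differ in risk): a = p/(1 − p), and q = 1 − ln(1 + a)/a.

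**Worked case, p = 50%, constant hazard.** H = 0.693; q = 1 − 0.5/0.693 = 0.279. At d = 15%: 0.85 × 0.5 + 0.15 × 0.279 = 0.467. With frailty, q = 1 − ln 2 = 0.307, giving 0.471.

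**Results.** The odds ratio is the arm with 20% dropout over the arm with 10%.

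| True p | Model | q | Reported, d = 15% | d = 10% | d = 20% | Gap (points) | OR |
|---|---|---|---|---|---|---|---|
| 20% | constant | 0.104 | 18.6% | 19.0% | 18.1% | 1.0 | 0.94 |
| 20% | frailty | 0.107 | 18.6% | 19.1% | 18.1% | 0.9 | 0.94 |
| 50% | constant | 0.279 | 46.7% | 47.8% | 45.6% | 2.2 | 0.91 |
| 50% | frailty | 0.307 | 47.1% | 48.1% | 46.1% | 1.9 | 0.92 |
| 90% | constant | 0.609 | 85.6% | 87.1% | 84.2% | 2.9 | 0.79 |
| 90% | frailty | 0.744 | 87.7% | 88.4% | 86.9% | 1.6 | 0.87 |

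With the same d and the same timing in both arms, the two expressions are identical and the OR is 1.00.

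**0-12 week window.** The shortfall is smaller, because only 15% × 12/26 = 6.9% have stopped by Week 12. For p = 50% at 26 weeks (constant hazard), the 12-week cumulative hazard is 0.693 × 12/26 = 0.320 and the true 12-week incidence is 27.4%. A stopper in that window has q = 1 − 0.274/0.320 = 0.144, so the reported value is 0.931 × 0.274 + 0.069 × 0.144 = 26.5%.

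**False-positive rate at nominal 5%.** Simulation with 283 versus 142 patients and 10% versus 20% dropout gave 6.4 to 8.4% for p of 35 to 70%, and 8 to 14% at 90%. A log-rank test on the same data gave 4.6 to 5.8%. The simulated stopping was independent of events, which is the condition the log-rank test needs.

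**Sensitivity.** A separate calculation used negative binomial events and 283 per arm. With 10% versus 20% dropout but all stopping in the first quarter of the period, the OR was 0.87 at 2 events per patient-year and 0.73 at 20, with rejection rates of 12.4% and 27.5%. For severe events at 10 per 100 patient-years with uniform stopping, incidence was 4.6% versus 4.4% (OR 0.95, rejection 5.2%).

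**The case against.** The strongest reply is that the plan already has an exposure-adjusted answer. The rate of the same events, named in the same objectives, uses an exposure offset. Imbalance would also be visible: reasons for discontinuing treatment and study are compared between arms (SAP 5.6), and exposure is summarized by duration (SAP 5.12.1). These endpoints lie outside the gatekeeping sequence and carry no multiplicity control (SAP 5.5), so no controlled claim depends on them. A crude on-treatment percentage is a legitimate description. All of this stands and limits the weight of the point. It does not make the crude percentage a 26-week risk, nor its odds ratio robust to unequal time on IP.

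A reader might infer that anyone who stops early counts as event-free. That is not so: a patient with an on-IP event before stopping counts as an event, and where events are frequent most stoppers will already have had one (q = 0.61 to 0.74 at p = 90%).

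A reader might also infer that the plan favors LY900014+20. The documents do not support this. They assume one dropout rate for all arms and give no reason to expect more stopping in that arm. The 10% versus 20% split is only an illustration. The direction also requires stopping to be unrelated to hypoglycemia; patients who stop because of an event are counted as events.

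Finally, censoring at IP stop needs its own independence assumption, which is doubtful if glycemic problems drive stopping. That argues against replacing the logistic model, but not against adding a second analysis.

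**Conclusion.** The point holds in a limited form. The incidence analyses ignore time on IP, and nothing in the protocol or SAP corrects this. Each arm's percentage understates on-treatment incidence over its window: by about 1 to 4 points at 26 weeks under 15% uniform stopping, for true incidence of 20% to 90%.

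Between-arm bias under equal risk arises only if the amount or timing of IP stopping differs. At an assumed 10% versus 20% with uniform stopping, the OR is about 0.79 to 0.94 and the gap is at most about 3 points. The 0.79 requires 90% incidence with no variation in risk between patients; with frailty it is 0.87. Early stopping would enlarge the effect. Event rates, splits and timings are all assumptions.

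The exposure-adjusted rate is not affected in this way, so the hypoglycemia conclusion is partly protected. The case is for a cheap supplementary analysis, not for calling the safety comparison invalid.

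**What to change.** Keep the crude percentage and the logistic model. In SAP Table ITSB.5.4, prespecify beside them, for the non-severe categories:

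- time to first event from the first IP dose, censored at the last on-IP date as SAP 5.1 defines it for diary events;
- a treatment comparison by Cox regression with treatment and age group, or a log-rank test stratified by age group;
- Kaplan-Meier percentages with an event by arm at Weeks 12 and 26;
- a sentence saying that crude incidence is to be read together with these percentages and the exposure-adjusted rate;
- a statement that the analysis assumes stopping IP is independent of hypoglycemia risk.

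Severe events can stay as planned. The effect there is small under the rate assumed above, and severe events are also SAEs, which SAP Table ITSB.5.3 summarizes to Visit 801 regardless of IP use.

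The cost is SAP text and some programming. Diary events already carry exact dates, and the SAP already plans Kaplan-Meier plots for TEAEs. The drawbacks are a second effect measure (a hazard ratio beside the odds ratio) and the independence assumption.
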